5.5.2 Methods of sample collection

5.5.2.1 Plasma sampling for pharmacokinetic analysis

For the quantification of analyte plasma concentrations, approximately 2.5 mL of blood will be taken from a forearm vein into a K3EDTA (ethylenediaminetetraacetic acid)

anticoagulant blood-drawing tube at the time points listed in the [Flow chart 1](#), [Flow chart 2](#) and [Flow chart 3](#) under PK sampling.

The blood samples must be taken from the forearm vein that is not receiving the i.v. infusion.

Mix the K₃EDTA-anticoagulated blood samples gently and place on ice until centrifugation at approximately +4°C. The blood will be centrifuged to produce plasma as soon as possible after collection, but not later than 30 minutes after withdrawal.

Centrifugation will last for approximately 10 minutes (at 2000 x g to 4000 x g) at approximately +4°C. Two aliquots of EDTA plasma samples will be obtained in two labelled (label to include: trial number, patient number, visit, PTM, aliquot 1 or 2, plasma, and PK) polypropylene cryotubes. The two aliquots should contain approximately 0.5 mL of plasma each. The plasma samples will be stored in a freezer set to -20°C or below at the clinical site(s) until shipment on dry ice to the central lab (with dry ice sufficient for 3 days transit), then stored in a freezer set to -70°C or below at the central lab until shipment to the analytical laboratory. Both aliquots will be shipped (in separate shipments with dry ice sufficient for 3 days transit) to the analytical laboratory for the determination of BI 655066/ABBV-066 (risankizumab). Both aliquots will be stored in a freezer set to -70°C or below at the analytical laboratory until the finalization of the clinical trial report.

5.5.2.2 Plasma sampling for assessment of anti-drug antibody

For the assessment of anti-drug antibody, approximately 2.5 mL of blood will be taken from a forearm vein into a K₃EDTA (ethylendiaminetetraacetic acid) anticoagulant blood-drawing tube at the time points listed in the [Flow chart 1](#), [Flow chart 2](#) and [Flow chart 3](#) under anti-drug antibody (ADA).

Mix the K₃EDTA-anticoagulated blood samples gently and place on ice until centrifugation at approximately +4°C. The blood will be centrifuged to produce plasma as soon as possible after collection, but not later than 30 minutes after withdrawal.

Centrifugation will last for approximately 10 minutes (at 2000 x g to 4000 x g) at approximately +4°C. Two aliquots of EDTA plasma samples will be obtained in two labelled (label to include: trial number, patient number, visit, PTM, aliquot 1 or 2, plasma, and ADA) polypropylene cryotubes. Both aliquots will contain approximately 0.5 mL of plasma each. The plasma samples will be stored in a freezer set to -20°C or below at the clinical site(s) until shipment on dry ice to the central lab (with dry ice sufficient for 3 days transit), then stored in a freezer set to -70°C or below at the central lab until shipment to the analytical laboratory. Both aliquots will be shipped (in separate

shipments with dry ice sufficient for 3 days transit) to the analytical laboratory for assessment of potential ADA to BI 655066/ABBV-066 (risankizumab). Following the finalization of the ADA bioanalytical report, selected ADA aliquots will be transferred to long term storage for possible/ additional ADA characterization in the future.

5.5.3 Analytical determinations

BI 655066/ABBV-066 (risankizumab) concentrations will be determined by a validated Enzyme Linked Immunosorbent Assay (ELISA).

The presence of ADA to BI 655066/ABBV-066 (risankizumab) will be assessed via a tiered approach using a validated electrochemiluminescence assay (screening, confirmatory, and titration analysis as appropriate). Samples that are confirmed positive will then be characterized in a validated neutralizing antibody (Nab) assay.

5.6 BIOMARKER(S)

5.6.1 Endpoints based on biomarker(s)

Biomarkers associated with Crohn's disease and the IL-23 pathway will be assessed in serum from patients' pre and post treatment with BI 655066/ABBV-066 (risankizumab). Changes in protein levels of disease specific markers such as but not limited to β defensin 2, neutrophil gelatinase associated lipocalin (NGAL), and S-100 proteins (A7, A8, A12) pre and post treatment with BI 655066/ABBV-066 (risankizumab) will be assessed. These biomarkers are considered exploratory and respective assays will be qualified to meet the required performance criteria.

Serum samples will be collected at time points indicated in [Flow chart 1](#), [Flow chart 2](#) and [Flow chart 3](#) for the analysis of biomarkers. After completion of the study these samples may be used for not yet specified non-genetic biomarker analyses associated with autoimmune diseases as well as method development and evaluation. Samples will be stored for a maximum of 3 years (under consideration of local legislation) upon signature of the final study report.

5.6.2 Methods of sample collection

For the assessment of soluble biomarkers in serum, approximately 8.5 ml of blood will be collected from a forearm vein into a serum separation tube at time points indicated in [Flow chart 1](#), [Flow chart 2](#) and [Flow chart 3](#). The blood will be thoroughly mixed with clotting activation agent by gently inverting the tube not less than five times and will be allowed to clot for at least 30 mins, but for a maximum of 60 mins, with the tube standing

upright. The tube is then centrifuged at 1500 to 2000 xg for 15 mins until clot and serum are separated by a well formed barrier. The serum will then be divided into at least 6 aliquots (in polypropylene tubes) of at least 500 μ l and will be frozen immediately at approximately -20°C or below until shipment on dry ice.

5.6.3 Analytical determinations

Characteristics of the analytical methods for the analysis of serum biomarkers will be given in detail in the clinical trial report.

5.7 PHARMACODYNAMICS

5.7.1 Pharmacodynamic endpoints

Serum will be collected to assess changes in the levels of IL-23 pathway and disease specific markers as stated in [Section 5.6.1](#).

5.7.2 Methods of sample collection

See Section 5.6.2

5.8 PHARMACOKINETIC - PHARMACODYNAMIC RELATIONSHIP

No formal analysis of pharmacokinetic/pharmacodynamic relationships is planned. If the data suggest a pharmacokinetic/pharmacodynamic relationship of special parameters, eg., CDAI, an exploratory analysis may be performed.

Correlation between drug concentration and response may be made if adequate data are available. In addition, exploratory correlations may also be made between drug concentration and AEs.

Data may also be used to develop pharmacokinetic/pharmacodynamic models using nonlinear mixed effect modeling techniques, if feasible. For this purpose data may also be combined with data from other trials. Modeling activities will be planned and documented separately according to internal and external guidelines and SOP.

6. INVESTIGATIONAL PLAN

6.1 VISIT SCHEDULE

All patients are to adhere to the visit schedule as specified in the [Flow chart 1](#), [Flow chart 2](#) and [Flow chart 3](#). Additional unscheduled visits for the purpose of re-testing of laboratory parameters or AE monitoring may be included as deemed necessary by the investigator.

For detailed description of the further trial procedures, please refer to the [Flow chart 1](#), [Flow chart 2](#) and [Flow chart 3](#).

6.2 DETAILS OF TRIAL PROCEDURES AT SELECTED VISITS

6.2.1 Screening period

After patients have been informed about the study, written informed consent in accordance with GCP and local legislation must be obtained prior to any study related procedures taking place. Patients will be assigned a number and enrolment must be recorded in eCRF pages.

Visit 1 of this study should preferably be performed in one visit combined with the last visit of preceding trial 1311.6 or during the interim period of maximum 5 days after completion of the last visit in 1311.6.

Patients rolling-over directly from preceding 1311.6 trial eligibility will be assessed based on the patient diary dispensed earlier at the 1311.6 trial containing symptoms over 7 days. Investigators will review the diary in order to assess the CDAI score. The hematocrit result to calculate the CDAI score must be used from visit 1. If an EoT (or at the last preceding trial visit E1 or E5) colonoscopy has not been performed during 1311.6, it must be performed between V1 and V2 in 1311.20/M15-989.

Patients successfully completing the 1311.6 trial before initiation of the 1311.20/M15-989 trial, will be assessed for eligibility based on a newly dispensed patient diary at visit 1. At the following 1.1 visit the investigator will review the diary in order to assess the CDAI score. The hematocrit result to calculate the CDAI score must be used from visit 1. If an EoT colonoscopy has not been performed during 1311.6 or if the patient had a treatment interruption followed by a clinical relapse, it must be performed between V1 and V2 in 1311.20/M15-989.

For detailed description of the trial procedures at screening please refer to [Flow chart 1](#), [Flow chart 2](#) and [Flow chart 3](#).

6.2.2 Treatment periods

If upon completion of screening patient eligibility was confirmed by maintaining clinical response or remission (CDAI drop ≥ 100 from baseline of 1311.6 or CDAI < 150) patients can directly be assigned to open label s.c. maintenance treatment (see [Flow charts 1](#) and [Flow chart 2](#)).

However, if clinical response or remission has been lost after end of treatment in 1311.6 and/or at screening for 1311.20/M15-989, patients will receive open label i.v. re-induction treatment with three infusions of 600 mg each every 4 weeks. After re-induction eligibility will be re-assessed. If clinical response or remission compared to 1311.20/M15-989 study entry is achieved patients will switch to s.c. maintenance treatment (see [Flow chart 3](#)).

During the s.c. maintenance treatment patients will be administered BI 655066/ABBV-066 (risankizumab) 180 mg every 8 weeks. Medication will be assigned by IRT. All study medication will be stored and administered on site by authorized study staff only.

For details on the study assessments refer to [Flow chart 1](#), [Flow chart 2](#) and [Flow chart 3](#).

6.2.3 End of trial and follow-up period

The follow up period is 20 weeks after the last administration of study medication. Refer to [Flow chart 1](#), [Flow chart 2](#) and [Flow chart 3](#) for further details.

7. STATISTICAL METHODS AND DETERMINATION OF SAMPLE SIZE

7.1 STATISTICAL DESIGN - MODEL

This trial is a single group, open label extension study of BI 655066/ABBV-066 (risankizumab) in patients with moderately to severely active CD. The patients enrolled in this study are those that achieved clinical response to previous treatment with BI 655066/ABBV-066 (risankizumab). There will be no statistical testing performed.

7.2 NULL AND ALTERNATIVE HYPOTHESES

There is no formal statistical hypothesis test planned.

7.3 PLANNED ANALYSES

Descriptive analyses will be used to analyse the proportion of participants achieving the efficacy endpoints. The study is designed to gain extensive documentation of safety and efficacy.

7.3.1 Primary analyses

There are no primary analyses for efficacy.

7.3.2 Secondary analyses

There is no secondary analyse for efficacy.

Other efficacy endpoints will be summarized descriptively by visit. They will be tabulated and descriptive statistics will be provided.

Additional further endpoints may be defined in the Trial Statistical Analysis Plan (TSAP).

7.3.3 Safety analyses

Since the main objective of this study is long term safety, the primary focus would be on incidence of drug-related AE and serious infection.

Adverse events will be coded using the Medical Dictionary for Regulatory Activities (MedDRA) coding dictionary. Summary tables and listings will be produced. All adverse events with an onset between start of treatment and end of the residual effect period (REP), a period of 20 weeks after the last dose of trial medication, will be assigned to the treatment period for evaluation.

All treated patients will be included in the safety analysis.

Statistical analysis and reporting of adverse events will concentrate on treatment-emergent adverse events. To this end, all adverse events occurring between start of treatment and end of the residual effect period will be considered 'treatment-emergent'. Adverse events that start before first drug intake and deteriorate under treatment will also be considered as 'treatment-emergent'. Frequency, severity, and causal relationship of adverse events will be tabulated by system organ class and preferred term after coding according to the current version of the Medical Dictionary for Drug Regulatory Activities (MedDRA). Safety analyses will focus on adverse events related to early discontinuation, immune suppression and injection site effects.

Laboratory data will be analysed both quantitatively as well as qualitatively. The latter will be done via comparison of laboratory data to their reference ranges. Values outside the reference range as well as values defined as clinically relevant will be highlighted in the listings. Treatment groups will be compared descriptively with regard to distribution parameters as well as with regard to frequency and percentage of patients with abnormal values or clinically relevant abnormal values. Analysis of laboratory measures will focus on haemotologic measures of immune suppression.

Vital signs, physical examinations, or other safety-relevant data observed at screening, baseline, during the course of the trial and at the end-of-trial evaluation will be assessed with regard to possible changes compared to findings before start of treatment.

7.3.4 Interim analyses

No formal interim analyses are planned. However since this is an open label study, interim analyses may be performed as needed after approximately 20 patients complete the study.

7.3.5 Pharmacokinetic analyses

Refer to [Section 5.5.1](#) for pharmacokinetic parameters to be calculated using noncompartmental analysis (NCA). The derivation of pharmacokinetic parameter is described in sponsor's standard operating procedure.

All evaluable patients who received at least one dose of BI 655066/ABBV-066 (risankizumab) will be included in the pharmacokinetic analysis. Patients who are considered as not evaluable will be listed with their individual plasma concentrations and individual pharmacokinetic parameters, however, will not be included in descriptive statistics for plasma concentrations, pharmacokinetic parameters or other statistical assessment.

Concentrations will be used for graphs and calculations in the format that is reported in the bioanalytical report. Noncompartmental pharmacokinetic analyses of the plasma concentration-time data will be performed using a validated software program. Only concentrations within the validated concentration range will be used for the calculation of pharmacokinetic parameters.

Plasma concentrations will be plotted graphically versus time for all evaluable patients as listed in the drug plasma concentration-time tables. The actual sampling times will be used for individual drug plasma concentration-time plots. For the presentation of the mean profiles, the arithmetic mean and the planned blood sampling times will be used.

The following descriptive statistics will be calculated for BI 655066/ABBV-066 (risankizumab) concentrations as well as for all pharmacokinetic parameters: N, arithmetic mean, standard deviation, minimum, median, maximum, arithmetic coefficient of variation, geometric mean, and geometric coefficient of variation. The data format for descriptive statistics of concentrations will be identical with the data format of the respective concentrations. The descriptive statistics of pharmacokinetic parameters will be calculated using the individual values with the number of decimal places as provided by the evaluation program. Then the individual values as well as the descriptive statistics will be reported with three significant digits in the clinical trial report.

7.3.6 Pharmacodynamic analyses

Baseline levels and changes from baseline in serum protein biomarkers will be described over time. Correlations between change from baseline in CDAI scores, endoscopic scores and biomarker levels will be explored. In addition, the relationships, between drug concentrations, clinical efficacy, and selected biomarkers will be explored. The details of these analyses will be included in the SAP.

7.3.7 Pharmacogenomic analyses

Not applicable.

7.4 HANDLING OF MISSING DATA

No imputation will be performed for missing data.

7.5 RANDOMISATION

There is no randomisation for this study. All patients will be assigned to the same regimen and dose of BI 655066/ABBV-066 (risankizumab) , regardless of the treatment and dose received in the 1311.6 trial.

7.6 DETERMINATION OF SAMPLE SIZE

The sample size is determined by the completion of previous trial and the consenting for the extension.

8. INFORMED CONSENT, DATA PROTECTION, TRIAL RECORDS

The trial will be carried out in compliance with the protocol, the principles laid down in the Declaration of Helsinki, in accordance with the ICH Harmonised Tripartite Guideline for Good Clinical Practice (GCP) and relevant AbbVie Standard Operating Procedures (SOPs). Standard medical care (prophylactic, diagnostic and therapeutic procedures) remains in the responsibility of the treating physician of the patient.

The investigator should inform the sponsor immediately of any urgent safety measures taken to protect the study subjects against any immediate hazard, and also of any serious breaches of the protocol/ICH GCP.

The rights of the investigator and of the sponsor with regard to publication of the results of this trial are described in the investigator contract. As a general rule, no trial results should be published prior to finalisation of the Clinical Trial Report.

Insurance Cover: Insurance certificates are made available to the investigator and the patients via documentation in the ISF (Investigator Site File).

8.1 STUDY APPROVAL, PATIENT INFORMATION, AND INFORMED CONSENT

This trial will be initiated only after all required legal documentation has been reviewed and approved by the respective Institutional Review Board (IRB) / Independent Ethics Committee (IEC) and competent authority (CA) according to national and international regulations. The same applies for the implementation of changes introduced by amendments.

Prior to patient participation in the trial, written informed consent must be obtained from each patient (or the patient's legally accepted representative) according to ICH GCP and to the regulatory and legal requirements of the participating country. Each signature must be personally dated by each signatory and the informed consent and any additional patient-information form retained by the investigator as part of the trial records. A signed copy of the informed consent and any additional patient information must be given to each patient or the patient's legally accepted representative.

The patient must be informed that his/her personal trial-related data will be used by AbbVie in accordance with the local data protection law. The level of disclosure must also be explained to the patient.

The patient must be informed that his / her medical records may be examined by authorised monitors (CML/CRA) or Clinical Quality Assurance auditors appointed by AbbVie by appropriate IRB / IEC members, and by inspectors from regulatory authorities.

8.2 DATA QUALITY ASSURANCE

A quality assurance audit/inspection of this trial may be conducted by the sponsor or sponsor's designees or by IRBs/IECs or by regulatory authorities. The quality assurance auditor will have access to all medical records, the investigator's trial-related files and correspondence, and the informed consent documentation of this clinical trial.

8.3 RECORDS

Case Report Forms (CRFs) for individual patients will be provided by the sponsor via remote data capture. For drug accountability, refer to [Section 4.1.8](#).

8.3.1 Source documents

Source documents provide evidence for the existence of the patient and substantiate the integrity of the data collected. Source documents are filed at the investigator's site.

Data entered in the eCRFs that are transcribed from source documents must be consistent with the source documents or the discrepancies must be explained. The investigator may need to request previous medical records or transfer records, depending on the trial; also current medical records must be available.

For eCRFs all data must be derived from source documents.

8.3.2 Direct access to source data and documents

The investigator / institution will permit trial-related monitoring, audits, IRB / IEC review and regulatory inspection, providing direct access to all related source data / documents. CRFs/eCRFs and all source documents, including progress notes and copies of laboratory and medical test results must be available at all times for review by the sponsor's clinical trial monitor, auditor and inspection by health authorities (e.g. FDA). The Clinical Research Associate (CRA) / on site monitor and auditor may review all CRFs/eCRFs, and written informed consents. The accuracy of the data will be verified by reviewing the documents described in Section 8.3.1.

8.4 LISTEDNESS AND EXPEDITED REPORTING OF ADVERSE EVENTS

8.4.1 Listedness

To fulfil the regulatory requirements for expedited safety reporting, the sponsor evaluates whether a particular adverse event is "listed", i.e. is a known side effect of the drug or not. Therefore a unique reference document for the evaluation of listedness needs to be provided. The current versions of the Investigator's Brochure reference documents are to be provided in the ISF. No AEs are classified as listed for study design, or invasive procedures.

8.4.2 Expedited reporting to health authorities and IECs/IRBs

Expedited reporting of serious adverse events, e.g. suspected unexpected serious adverse reactions (SUSARs) to health authorities and IECs/IRBs, will be done according to local regulatory requirements. Further details regarding this reporting procedure are provided in the Investigator Site File.

8.6 COMPLETION OF TRIAL

The EC/competent authority in each participating EU member state needs to be notified about the end of the trial (last patient/patient out, unless specified differently in [Section 6.2.3](#) of the CTP) or early termination of the trial.

10. APPENDICES

- [Appendix 10.1](#) Clinical evaluation of liver injury
- [Appendix 10.2](#) Equivalent doses of corticosteroids
- [Appendix 10.3](#) Severity of AE as described in the Rheumatology Common Toxicity Criteria (RCTC) Version 2.0 (OMERACT)

10.1 CLINICAL EVALUATION OF LIVER INJURY

10.1.1 Introduction

Alterations of liver laboratory parameters, as described in [Section 5.2.2.1](#) (Adverse Events of Special Interest), are to be further evaluated using the following procedures:

10.1.2 Procedures

Repeat the following laboratory tests: ALT, AST, and bilirubin (total and direct) - within 48 to 72 hours and provide additional blood sample to the central laboratory for automatic reflex testing of the below listed laboratory parameters. Only in case whereby the central laboratory is not immediately available (e.g. if the logistics are such that the patient's repeat specimen would not reach the central laboratory in a reasonable timeframe), ALT, AST, and bilirubin (total and direct) will be evaluated by local laboratory and results are made available to the investigator and to BI as soon as possible. If in such a case ALT and/or AST ≥ 3 fold ULN combined with an elevation of total bilirubin ≥ 2 fold ULN are confirmed, results of the laboratory parameters described below must be made available to the investigator and to BI as soon as possible.

Clinical chemistry

alkaline phosphatase, albumin, PT or INR, CK, CK-MB, coeruloplasmin, α -1 antitrypsin, transferin, amylase, lipase, fasting glucose, cholesterol, triglycerides

Serology

Hepatitis A (Anti-IgM, Anti-IgG), Hepatitis B (HbsAg, Anti-HBs, DNA), Hepatitis C (Anti-HCV, RNA if Anti-HCV positive), Hepatitis D (Anti-IgM, Anti-IgG), Hepatitis E (Anti-HEV, Anti-HEV IgM, RNA if Anti-HEV IgM positive), Anti-Smooth Muscle antibody (titer), Anti-nuclear antibody (titer), Anti-LKM (liver-kidney microsomes) antibody, Anti-mitochondrial antibody
<project dependent:> Epstein Barr Virus (VCA IgG, VCA IgM), cytomegalovirus (IgG, IgM), herpes simplex virus (IgG, IgM), varicella (IgG, IgM), parvovirus (IgG, IgM), toxoplasmosis (IgG, IgM)>

Hormones, tumormarker

TSH

Haematology

Thrombocytes, eosinophils

- Provide abdominal ultrasound to rule out biliary tract, pancreatic or intrahepatic pathology, e.g. bile duct stones or neoplasm.
- Initiate close observation of subjects by repeat testing of ALT, AST, and total bilirubin (with fractionation by total and direct) at least weekly until the laboratory ALT and / or AST abnormalities stabilize or return to normal, then according to the protocol. Depending on further laboratory changes, additional parameters identified e.g. by reflex testing will be followed up based on medical judgement and Good Clinical Practices (GCP).

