defect, or is to be deemed serious for any other reason if it is an important medical event when based upon appropriate medical judgement which may jeopardise the patient and may require medical or surgical intervention to prevent one of the other outcomes listed in the above definitions.

Medical and scientific judgment should be exercised in deciding whether other situations should be considered serious reactions, such as important medical events that might not be immediately life threatening or result in death or hospitalisation but might jeopardise the patient or might require intervention to prevent one of the other outcomes listed above.

Examples of such events are intensive treatment in an emergency room or at home for allergic bronchospasm, blood dyscrasias or convulsions that do not result in hospitalisation or development of dependency or abuse. Any suspected transmission via a medicinal product of an infectious agent is also considered a serious adverse reaction.

Life-threatening in this context refers to an event in which the patient was at risk of death at the time of the event; it does not refer to an event that hypothetically might have caused death if more severe.

Adverse Events of Special Interest (AESI)

The term AESI relates to any specific AE that has been identified at the project level as being of particular concern for prospective safety monitoring and safety assessment within this trial, e.g. the potential for AEs based on knowledge from other compounds in the same class. AESI need to be reported to the Sponsor's Pharmacovigilance Department within the same timeframe that applies to SAE, see [Section 5.2.2.2](#).

The following are considered as AESI:

- Hepatic injury defined by the following alterations of liver parameters:
 - For patients with normal liver function at baseline: an elevation of aspartate aminotransferase (AST) and/or alanine aminotransferase (ALT) ≥ 3 fold upper limit of normal (ULN) combined with an elevation of total bilirubin ≥ 2 fold ULN measured in the same blood draw sample.
 - Hepatic injury defined by the following alterations of liver parameters (for patients with impaired liver function tests at baseline): an elevation of AST and/or ALT ≥ 3 times the baseline value combined with an elevation of bilirubin ≥ 2 times the baseline value measured in the same blood draw sample.

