Patients showing these lab abnormalities need to be followed up according to [Section 10.1.2](#) of this clinical trial protocol and the hepatic injury adverse event form provided via EDC system. These lab findings constitute a hepatic injury alert and the patients showing these lab abnormalities need to be followed up according to the hepatic injury AE form via the EDC-system. In case of clinical symptoms of hepatic injury (icterus, unexplained encephalopathy, unexplained coagulopathy, right upper quadrant abdominal pain, etc.) without lab results (ALT, AST, total bilirubin) available, the investigator should make sure these parameters are analysed, if necessary in an unscheduled blood test. Should the laboratory results meet the definition of hepatic injury, the investigator will complete the supplemental form. **Cardiac Events/Procedures**

In the case of any of the following reported major cardiovascular adverse events (MACE), the appropriate supplemental eCRFs should be completed:

- Cardiac events;
- Myocardial infarction or unstable angina;
- Cerebral vascular accident and transient ischemic attack;
- Cardiovascular procedures

Tuberculosis (TB)

In the case of any positive TB test or diagnosis of active TB, the appropriate supplemental eCRF should be completed.

Intensity of adverse event

The intensity grading of AEs will be performed according to Rheumatology Common Toxicity Criteria (RCTC) Version 2.0 developed by OMERACT ([R13-3515](#)). See [Appendix 10.3](#) for intensity/severity classification.

Causal relationship of adverse event

The definition of an adverse reaction implies at least a reasonable possibility of a causal relationship between a suspected medicinal product and an adverse event. An adverse reaction, in contrast to an adverse event, is characterised by the fact that a causal relationship between a medicinal product and an occurrence is suspected.

Medical judgment should be used to determine the relationship, considering all relevant factors, including pattern of reaction, temporal relationship, de-challenge or re-challenge,

confounding factors such as concomitant medication, concomitant diseases and relevant history.

Arguments that may suggest that there is a reasonable possibility of a causal relationship could be:

- The event is consistent with the known pharmacology of the study drug.
- The event is known to be caused by or attributed to the drug class.

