RSI in place at the time of occurrence of the 'suspected' Serious Adverse Reaction will be used to assess expectedness.

Information required

The following should also be recorded as an (S)AE in the (e)CRF and SAE form (if applicable):

- Worsening of the underlying disease or of other pre-existing conditions
- Changes in vital signs, ECG, physical examination and laboratory test results, if they are judged clinically relevant by the investigator

If such abnormalities already pre-exist prior trial inclusion they will be considered as baseline conditions.

All (S)AEs, including those persisting after individual patient's end of trial must be followed to a satisfactory conclusion or no further information can be obtained.

Pregnancy

Pregnancy in a study subject must be reported to AbbVie within 1 working day of the site becoming aware of the pregnancy. Subjects who become pregnant during the study must be discontinued from study drug.

Information regarding a pregnancy occurrence in a study subject and the outcome of the pregnancy will be collected.

Pregnancy in a study subject is not considered an AE. However, the medical outcome of an elective or spontaneous abortion, stillbirth, or congenital anomaly is considered an SAE and must be reported to AbbVie within 24 hours of the site becoming aware of the event.

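### The fixed weekly liver-test interval in Protocol 10.1.2 ends on ALT/AST alone, although the hepatic-injury alert also requires raised bilirubin; two fallback sentences still name the former sponsor

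*Protocol*

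**What the plan says.** Protocol 5.2.2.1 lists hepatic injury as an adverse event of special interest. For patients with normal liver function at baseline it requires AST and/or ALT of at least 3 times ULN "combined with an elevation of total bilirubin ≥ 2 fold ULN measured in the same blood draw sample". For patients with impaired liver tests at baseline, the multiples (3 and 2) apply to the baseline values instead. The section adds: "These lab findings constitute a hepatic injury alert". It sends these patients to Appendix 10.1.2 and to a hepatic injury form in the EDC system.

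Appendix 10.1.2 then asks for close observation with ALT, AST and total bilirubin "at least weekly until the laboratory ALT and / or AST abnormalities stabilize or return to normal, then according to the protocol".

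The same appendix has a local-laboratory fallback, which applies "Only in case whereby the central laboratory is not immediately available". Its first sentence says that "results are made available to the investigator and to BI as soon as possible". Its second, for confirmed cases, says that "results of the laboratory parameters described below must be made available to the investigator and to BI as soon as possible". Protocol 3.1.1 names AbbVie as sponsor, and SAP 11.0 describes the transfer of responsibilities from Boehringer Ingelheim.

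**The concern.** The alert needs two findings in one sample, transaminases and bilirubin. The rule that ends weekly testing looks at only one of them. A patient whose ALT and AST have settled while bilirubin is still rising meets the end condition as written.

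What is at stake is the timing of safety monitoring. Protocol 2.3 commits the study to timely follow-up of liver laboratory changes, and 10.1.2 is where that commitment becomes a schedule. Once the weekly rule ends, the remaining rules require follow-up but state no frequency.

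The BI wording is a separate and smaller matter: urgent fallback results are addressed to a company that no longer sponsors the trial.

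**Working it through.** No statistical formula applies; the trial is descriptive. The check compares the rules and then reads the visit spacing from the flow charts.

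**Rules side by side**

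| Rule | Source | Bilirubin covered? | Interval stated? |
|---|---|---|---|
| Alert definition | Protocol 5.2.2.1 | Yes, required | Not applicable |
| Weekly tests, analytes | Protocol 10.1.2 | Yes, measured | At least weekly |
| Weekly tests, end condition | Protocol 10.1.2 | No, ALT/AST only | Weekly rule ends here |
| Further parameters | Protocol 10.1.2, next sentence | Left to medical judgement | No |
| Repeats of clinically relevant abnormal results | Protocol 5.2.3 | Yes, if judged relevant | No |
| (S)AE follow-up: "must be followed to a satisfactory conclusion or no further information can be obtained" | Protocol 5.2.2.2 | Yes, as part of the event | No |
| Unscheduled retest visits | Protocol 6.1 | Possible | No |

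The only fixed timing left after the weekly rule is the visit schedule.

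**Wait to the next scheduled laboratory test**

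Maximum wait = nominal spacing + late window of the later visit + early window of the earlier visit. Mean wait = half the nominal spacing, if the weekly rule ends at a uniformly random point between visits (an assumption).

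- S.c. maintenance: visits every 8 weeks, windows ±7 days. Nominal 8 × 7 = 56 days; maximum 56 + 7 + 7 = 70; mean 56 / 2 = 28.
- I.v. re-induction (Flow chart 3, Visits 2 to 5, windows ±7, ±5, ±5, ±7): nominal 4 × 7 = 28 days. Maximum 28 + 7 + 5 = 40 for Visits 2–3 and 4–5, and 28 + 5 + 5 = 38 for Visits 3–4; mean 28 / 2 = 14. The flow-chart tables are broken in the text, but SAP Table 6 has laboratory windows at i.v. Weeks 0, 4 and 8, which supports the 28-day spacing.
- After stopping study drug (Protocol 3.3.4.1): flow-chart footnote 3 gives an early EoT visit, which includes laboratory tests, and then a call 140 days after the last dose. Scheduled laboratory tests after that visit: 0.

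Retests under Protocol 5.2.2.2 and 5.2.3 come in between, at no stated interval.

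**Recipient**

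Both fallback sentences (2 of 2) name BI. The default central-laboratory route is not affected.

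**Effect on the analyses**

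SAP 10.3 uses central and local laboratory data. SAP 10.3.1 lists potential Hy's Law cases from the values themselves. SAP 10.3.2 lists a parameter's whole course for values at CTC Grade 3 or above that exceed the baseline grade. None of these depends on the weekly rule, and no effect on them is shown.

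**The case against.** The strongest reply is that the case is already covered. Bilirubin is measured at every weekly draw, so the investigator sees it. A value of 2.0 to 3.0 times ULN is graded severe in Protocol Appendix 10.3. After a hepatic-injury alert it would hardly be judged irrelevant, so 5.2.3 would require repeats until it normalises, stabilises or is explained. Section 6.1 allows unscheduled retest visits. On this view the plan leaves timing to clinical judgement once transaminases settle, and a fixed interval is a preference. The EDC hepatic injury form, which is not among the documents, might also state an interval. The 56- and 28-day figures are visit spacings, not expected gaps in bilirubin testing. The BI wording has no shown consequence, because special-interest events go to the sponsor's "Pharmacovigilance Department within the same timeframe that applies to SAE".

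Much of this stands. Follow-up does not stop, the day counts are upper limits on scheduled tests only, and the case still reaches AbbVie by the separate reporting route. But none of the cited rules states a frequency, and a form that cannot be read cannot be relied on to supply one. The protocol did choose a fixed interval for these patients and then ended it on half of the alert definition. That is a stated rule, not a missing detail.

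**Conclusion.** The concern holds and is minor. As written, the weekly interval can end while bilirubin is still abnormal and changing. The next scheduled test is then up to 56 days away on s.c. treatment (70 at the outer windows) and up to 28 days during re-induction (40 at the outer windows), with none scheduled after an early EoT visit. The averages of 28 and 14 days rest on the uniform-timing assumption.

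The documents give no rate of such cases; with about 60 patients few would be expected. No harm and no effect on the analyses is shown. The BI references are clerical: at most, fallback values could be misrouted or delayed.

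**What to change.** 1. In Protocol 10.1.2, change the end condition so that testing continues *at least weekly until ALT, AST and total bilirubin have all stabilised or returned to normal or to baseline*, and follows the visit schedule after that. The reference to baseline covers the patients with impaired liver tests whom 5.2.2.1 defines separately. Keeping stabilisation as an end point avoids indefinite weekly testing of a raised but steady bilirubin.
2. In both fallback sentences, replace BI with the sponsor (AbbVie Clinical Pharmacovigilance, by the contact route in 5.2.2.2).

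The cost is wording at three places in one appendix, with no new scheduled visits. Extra unscheduled draws arise only when bilirubin settles later than ALT and AST, one for each whole week of lag. The documents give no lag; an assumed 1 to 4 weeks means 1 to 4 draws per case.
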